Expected Results. Because there are limited data and no studies evaluating the short-term effects of CPT-C on CHD biomarkers, HRV was selected as the primary outcome based on our limited pilot data; the other CHD markers will be secondary outcomes. We hypothesize that all CHD biomarkers will show improvement following CPT-C when compared to WP-CON, and the changes will be independent of changes in cardiovascular health risk behaviors, as defined by smoking, alcohol use, and low physical activity measured using the Stanford 7-day physical recall survey (Blair et al., 1985). It is likely that these cardiovascular health behaviors will remain constant or minimally change over the time period of the study.

Analytic strategy. The primary CHD risk biomarker, HRV, and secondary CHD risk biomarkers are continuous measures collected at baseline and 7-weeks (post-treatment) and therefore the same modeling strategy will be used for all CHD biomarker outcomes. To test the primary hypothesis of a CPT-C effect at post-treatment, we will use a general linear model that accounts for the correlation between participants' repeated outcome measurements over time with an unstructured covariance matrix (Verbeke & Molenberghs, 2000; Fitzmaurice, Laird, & Ware, 2004). The general form of the model is $Y_{it} = X_{it}\beta + \epsilon_{it}$, where Y_{it} is the CHD marker for subject i at time t=0 and 7 weeks. The predictors (X_{it}) in the model will include time and the CPT-C arm by time interaction. We will estimate the model parameters using the SAS procedure MIXED (SAS Version 9, Cary, NC), and contrasts will be written in the context of this model to test the difference of mean change in CHD markers between the two treatment arms at week 7. For improvement in precision, the model will also be adjusted for

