stratification variables of gender, age, and comorbid major depressive disorder (Committee for Proprietary Medicinal Products, 2004) and as identified in the detailed description of methodologies and in the general analytic section, sensitivity analysis will also include the potential important covariates of functional comorbidity, smoking status, substance abuse, and habitual physical activity. Our main analysis technique for the primary outcome, general linear models via maximum likelihood estimation, uses all available data on subjects, rather than using only subjects with completely observed information, implicitly accommodating missingess when related to prior outcome, or to other baseline covariates included in the model (defined as missing at random).

Aim 2: To examine mechanisms of change in CHD risk biomarker outcomes in a mediation framework. It has been repeatedly demonstrated that individuals suffering from PTSD show excessive SNS, reduced PNS activity, chronic inflammation, and endothelial dysfunction and a number of studies have presented evidence suggestive of the possibility that these CHD markers of risk may be normalized following PTSD treatment (Cohen et al., 2000; Nishith et al., 2003; Blanchard et al.2002; Rabe et al., 2006; Hinton, Hofmann, Pollack, & Otto, 2009). The objective of this aim is to examine whether the change in PTSD symptoms explains the change in CHD biomarkers observed following CPT-C. To achieve this objective, we will test the working hypothesis that improvements in CHD risk biomarkers will be mediated by reductions in PTSD symptom severity. These findings will help establish whether PTSD symptoms themselves are determinants of CHD risk, independently of psychiatric comorbidity and health behaviors associated with cardiovascular risk. When the proposed studies for aim #2 have been completed, it is our expectation that the magnitude of the contribution of PTSD symptom load towards each of the evaluated CHD risk biomarkers will be clarified. Such a finding would be of importance, because it would provide support for a direct role of PTSD symptoms in the CHD risk observed in PTSD and would also identify which cardiac biomarker would provide the most utility in screening and CHD risk stratification in order to predict and prevent the onset of CHD.

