Approach. This RCT with repeated measurements of PTSD symptoms and CHD markers will provide a mechanism to evaluate the temporal relationship between the change in PTSD symptoms and the changes in ANS control mechanisms, endothelial function and inflammation. Using this temporal relationship, we will examine whether changes in PTSD symptoms mediate the effects of CPT-C on CHD markers.

Expected Results. We anticipate that the change in PTSD symptoms will mediate the relationship between CPT-C and CHD marker change, thereby identifying the role of reduction in PTSD symptoms as a mechanism for the improvement in CHD risk.

Analytic strategy. We propose to conduct mediation analyses using the more commonly known Baron and Kenny approach (Baron & Kenny, 1986) as well as the newer MacArthur approach (Kraemer, Kieser, Essex, & Kupler, 2008). By the MacArthur definition, the potential mediator must be during or post-treatment; therefore, the change in PTSD symptoms severity between week 0 and week 6 will be considered as a potential mediator. The outcome then will be participants' post-treatment change in CHD risk biomarkers, which will be determined at week 7. We will also explore the role of trajectories of change in PTSD symptom severity as a mediator of the post-treatment change in CHD risk biomarkers by deriving an individual-level summary measure of PTSD symptom change using the successive PTSD symptoms assessed at two week intervals. We will first fit a model to examine the relationship between the mediator (C) (i.e., change in PTSD symptoms during treatment) and

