treatment group: $C = \gamma_0 + \gamma_1^*$ treatment. We then fit a model examining the relationship between the mediator and post-treatment change in CHD biomarkers (Y): Y = β_0 + treatment* β_1 + C* β_2 . Finally, to show mediation, we will test that the product of γ_1 and β_2 is not equal to 0 using an extension of the Sobel first-order test (Fritz & MacKinnon, 2007); that is, the the effects of CPT-C on CHD risk biomarkers are attributable to its effects on PTSD symptom improvement. To fully understand these relationships, we will also investigate the MacArthur approach, where our second model will be (Y): Y = β_0 + treatment* β_1 + C* β_2 + C* treatment * β_3 . Under this approach, improvements in CHD biomarkers are attributable to improvements in PTSD symptoms if there is evidence that γ_1 is not equal to 0, and either β_2 or β_3 are not equal to zero. The model will also be adjusted for stratification variables of gender, age, and major depressive disorder, and as detailed above in the general analytic section in the sensitivity analysis, we will evaluate and include other potentially important covariates, including change in anxiety and depressive symptoms estimated from the changes in HADS anxiety and depression following the intervention. We will also explore an as-treated analysis to maximize the potential mediation effects of PTSD symptom severity changes over time. For these analyses, data will be deemed usable for any individual who drops out of the study after two weeks or more of CPT-C or WP-CON, if PTSD symptom change is available and a repeat CHD biomarker assessment can be performed after the PTSD symptom change is assessed.

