Analytic strategy. We will examine whether the effect of PTSD symptom severity changes on change in CHD risk biomarkers is moderated by patient characteristics of gender and major depressive disorder using the summary measure of PTSD symptom severity change that we defined in AIM 2 and the evaluating the outcome of the participants' post-treatment change in CHD risk biomarkers. We will fit a linear model including the predictors: PTSD symptom severity change, and the PTSD symptom severity change arm by moderator variable interaction (gender of major depressive disorder status) with the addition of covariates for baseline demographic and clinical characteristics. We will estimate 95% confidence intervals from these models for the difference in changes in CHD risk markers for PTSD symptom severity level changes by gender and depression status. As outlined in the section describing more detailed methodologies (C.4), the proposed design will also allow us to explore the role of a number of other patient characteristics as potential moderators of the association between change in PTSD symptom severity and change in CHD risk biomarkers (clinical anxiety disorder, socioeconomic status, and social support).

Potential Difficulties/Alternative Approaches. We anticipate that some participants will drop out of trauma focused therapy (CPT-C). In randomized clinical trials of CPT, drop-out rates have been 20-25% ([name], Nishith, Weaver, Astin, & Feuer, 2002; Chard, 2005). However, this is not likely to compromise our analytic approach for the following reasons: (i) we have structured our compensation system so that financial compensation is contingent upon completion of the PTSD and CHD biomarker

assessment, and not contingent upon completion of the full CPT-C treatment or control arm, and we will encourage participants who cease therapy to remain in the study to complete follow-up assessments; (ii) our analytic approach incorporates methods that are robust to incomplete data. In our recent study examining cardiovascular health risk biomarkers among younger adults with and without PTSD that included multiple laboratory sessions and measurement of 24-hour HRV our attrition rates were less than 10%.

B. METHODS

Participants

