administered at follow-up visits will be the weekly version, and participants will also be asked to report frequency of symptoms within the past month in order to establish PTSD caseness. Diagnoses other than PTSD, including major depressive disorder, generalized anxiety disorder, and panic disorder will be assessed using the Structured Clinical Interview (SCID) for DSM-5. Diagnostic raters will be trained using SCID and CAPS standardized training (i.e., manual, videotapes, and co-rating training with a trained rater). Interrater reliability for diagnoses based on videotapes of participant interviews across our previous studies has been high, Fleiss' kappa = .96. PTSD symptom severity will be measured by the PTSD Checklist (PCL5) with criterion A (Weathers, Litz et al., 2013). The PCL will be given at multiple time points (baseline, at each Holter monitoring time point, and at three time points during the treatment/waitlist period). On each of the days that the participant wears a Holter monitor, he/she will complete the PCL 5 and the Positive and Negative Affect Scale (PANAS; Watson, Clark et al., 1988). In addition, trauma history will be evaluated at baseline using the Traumatic Life Events Questionnaire (TLEQ), which collects the occurrence and frequency of each of 22 behaviorally-descriptive potential traumatic events and provides a 23rd open-ended category for "other events" (Kubany et al., 2000). The data provided by the TLEQ will primarily be used to describe the sample, but supplemental analyses will explore the role of trauma exposure chronicity and type as a moderator of the association between CPT-C and the change in CHD risk biomarkers. Participants will also complete the Posttraumatic Safety Behavior Scale (PSBS), which is a brief self-report measure of safety behaviors that persons with PTSD might perform to reduce distress associated with trauma. Psychological resilience will be measured using the Connor Davidson Resilience Scale (CD-RISC; Connor & Davidson, 2003), and interpersonal violence will be assessed using the Conflict Tactics Scale, version 2 (CTS2; Straus, Hamby, Boney-McCoy, & Sugarman, 1996). The presence of sleep problems will be measured using the Pittsburgh Sleep Quality Index with PTSD Addendum (PSQI-A; Buysse, Reynolds, Monk, Berman, & Kupfer, 1989; Germain, Hall, Krakow, Shear, & Buysse, 2005) and the STOP BANG, a measure of obstructive sleep apnea (Chung et al., 2008). The PSQI-A will be given at the Time 2 and Time 3 (if applicable) assessments because it is anticipated that sleep quality could change with treatment of PTSD symptoms. The Everyday Discrimination Scale will measure the perceived frequency of chronic, routine and subtle experiences of unfair treatment that could be one dimension of perceived stress in our sample (Williams, Yu, Jackson, & Anderson, 1997). Shame and guilt related to trauma will be measured by the Shame and Guilt After Trauma Scale (Aakvaag et al., 2016). Hostile interpretation bias will be measured by the Word Sentence Association Paradigm (WSAP; Dillon et al., 2016). At each CPT session, participants will complete the Assimilation Questionnaire, which measures assimilated beliefs and resulting emotions related to the trauma ([name], personal communication). At the beginning and end of CPT treatment, participants will complete several measures designed to examine cognitions - Cognitive Emotion Regulation Questionnaire, Trauma-Related Guilt inventory, Posttraumatic Cognitions Inventory, and Global Belief in a Just-World Scale.

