Suicidal and/or Homicidal Ideation. The Traumatic Stress and Health Research Laboratory (TSHRL) has established standards of practice for the evaluation of risk of suicide and homicide. The policy includes a thorough risk assessment including evaluation of risk factors and protective factors associated with both suicide and homicide. Also included in the policy are differential recommendations for action based on determinations of low, moderate, or high risk. Any staff member conducting an interview in which moderate or high risk is determined will contact a senior staff person with clinical expertise in risk assessment [including the PI, co-investigator(s), and/or DUMC's Emergency Room]. Although we are not selecting PTSD patients based upon their level of depressive symptoms, our assessments may determine the presence of severe depression. If patients are acutely suicidal, they will be evaluated and appropriate referral or admission procedures will be initiated, and they will be dropped from further study. At several time points throughout the study, participants are reminded that they are asked to inform the study therapist, study coordinator, or study PI if they experience a psychiatric emergency such as homicidal or suicidal ideation. In addition, participants are provided the telephone

number of study staff who they can call in the case of psychiatric emergencies, including an after-hours contact number.

Post-Study Referrals for Participants. It is not unexpected that participants may complete the study with residual PTSD and/or major depressive disorder symptoms. Because participants complete the PTSD Checklist (PCL5) and the Beck Depression Inventory -II (BDI-II) at multiple time points, we will refer to these scores at the end of the study as a gauge of residual symptoms. We will provide referrals for continued treatment to anyone with a score of 38 or higher on the PCL5 and/or a BDI-II score of 20 or higher (i.e., moderate to severe depression range). Additionally, referrals will be provided to participants who self-report distress at symptoms of PTSD or depression (regardless of measure scores) and wish to continue with another form of treatment.

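### Cheap improvement: separate safety withdrawal from study withdrawal, so that participants removed for acute suicidality after randomization are still offered the week-7 assessment

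*Combined protocol and SAP*

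**What the plan says.** The section on suicidal and homicidal ideation deals with severe depression found at study assessments. For patients who are acutely suicidal it states that "appropriate referral or admission procedures will be initiated, and they will be dropped from further study". The next sentence begins "At several time points throughout the study, participants are reminded that they are asked to inform the study therapist, study coordinator, or study PI" and concerns psychiatric emergencies, so the section also has people already in the study in view.

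Other places bear on what happens to their data:

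- **Outcome and timing (Aim 1, Expected Results and Analytic strategy).** "HRV was selected as the primary outcome based on our limited pilot data; the other CHD markers will be secondary outcomes". The biomarkers are measured at baseline and week 7 only.
- **Mediator (Aim 2, Analytic strategy).** "the change in PTSD symptoms severity between week 0 and week 6 will be considered as a potential mediator". The PCL-5 is also given "at three time points during the treatment/waitlist period" (PTSD and Psychiatric Evaluation).
- **Retention (Potential Difficulties/Alternative Approaches).** "we will encourage participants who cease therapy to remain in the study to complete follow-up assessments".
- **Dropouts (Aim 2, Analytic strategy).** In the as-treated mediation work, "data will be deemed usable for any individual who drops out of the study after two weeks or more of CPT-C or WP-CON", provided that symptom change is available and a later biomarker assessment is possible.
- **Missing data.** The likelihood model "uses all available data on subjects, rather than using only subjects with completely observed information", and the same strategy serves every CHD biomarker. The Missing Data section adds multiple imputation and pattern-mixture sensitivity analyses for the primary analysis.
- **A parallel rule (Interventions, WP-CON).** Control participants who call in distress during the six weeks and accept immediate therapy leave the study.

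**The concern.** The rule ends study participation, not just study treatment. HRV has one post-baseline value, so a participant removed before that visit contributes no follow-up HRV. The other biomarkers go with it, as do the post-treatment questionnaires and, for anyone removed before week 6, the week 0 to 6 PTSD change used as the mediator. PCL-5 scores taken before removal survive. Control participants removed during their deferred CPT-C already have their week-7 data.

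The reason for the loss is a clinical event after randomization, and it could plausibly be related to PTSD course and autonomic state. The primary model allows for missingness that depends on prior outcome or on baseline covariates in the model. A later suicidal crisis is neither. The General Analytic Strategies section commits to intent-to-treat, and the Missing Data section puts prevention first. Part of this loss could be prevented by offering the assessment.

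**Working it through.** **1. Which provisions reach a participant removed for safety?**

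- The retention sentence covers people who stop therapy. It does not mention people whom the study removes.
- The dropout sentence in Aim 2 covers leaving the study, which is closer. It needs at least two weeks in the arm, depends on a repeat assessment being possible, and neither schedules nor offers one. A value obtained under it would, however, enter the all-available-data model for Aim 1.
- Adverse-event follow-up to resolution (Data Safety and Monitoring Plan) follows the event, not the trial outcomes.

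So the documents show a general intent to keep collecting data, but no instruction to do so for this group.

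**2. Reproducing the plan's detectable effect.** Inputs from Power Analysis: 120 randomized (80 and 40), 80% power, alpha 0.05 (taken as two-sided), 20% attrition, rho 0.3 to 0.6.

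Evaluable: 80 × 0.80 = 64 and 40 × 0.80 = 32.

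d = 2.802 × √(1 − rho²) × √(1/n1 + 1/n2)

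| rho | d at 64/32 | Table 2 |
|---|---|---|
| 0.3 | 0.579 | 0.60 |
| 0.4 | 0.556 | 0.55 |
| 0.5 | 0.525 | 0.55 |
| 0.6 | 0.485 | 0.50 |

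Rounded to the nearest 0.05, all four agree with the plan.

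**3. How many people.** The documents give no rate. I assume 0% to 5% per arm:

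- CPT-C: 0.05 × 80 = 4 at most
- Control: 0.05 × 40 = 2 at most
- Total: 0 to 6, against 0.20 × 120 = 24 losses already planned for (6/24 = 25%)

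**4. Power.** In the worst case all 6 come on top of the 24, leaving 60 and 30:

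- rho 0.3: 2.802 × 0.954 × √(1/60 + 1/30) = 0.598, against 0.579
- rho 0.6: 2.802 × 0.800 × √(1/60 + 1/30) = 0.501, against 0.485

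The detectable effect rises by about 0.02 SD. At an effect of 0.60 and rho 0.3, power falls from 82.8% to 80.3% (normal approximation).

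**5. Bias.** Let p be the share of an arm removed (p1 for CPT-C, p2 for control). Let g be the removed-minus-retained difference in mean HRV, in SD units, beyond what the model explains (g1 and g2). Treat other losses as ignorable.

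Error in the CPT-C minus control contrast = −(p1 × g1 − p2 × g2)

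With p from 0 to 0.05 and |g| up to 1:

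- **Gaps of the same sign in both arms:** at most 0.05 × 1 = 0.05 SD either way. That is 2.0 units at SD 40 or 2.5 at SD 50. Against Table 2, 0.05/0.60 = 8% and 0.05/0.50 = 10%.
- **Gaps of opposite sign:** at most 0.05 + 0.05 = 0.10 SD, or 4 to 5 units. Against Table 2, 0.10/0.60 = 17% and 0.10/0.50 = 20%.
- **No removals, or equal rates and gaps:** 0.

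**The case against.** The strongest reply is that this hardly matters and that the text may not even apply. The removal sentence follows a remark about what assessments may reveal, and prominent ideation is already an entry exclusion. The reminder sentence does not say that those who report an emergency are removed. The section also summarizes a laboratory policy that may say more. Withdrawing an acutely suicidal person from research procedures is a defensible clinical choice. An HRV recording made around an admission may reflect crisis care rather than the assigned arm. Attrition of 20% is budgeted, and the missing-data plan is better than most.

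Much of this stands. Use of the rule after randomization is the natural reading, not an explicit statement. The case count is likely very low. Likelihood estimation covers the secondary biomarkers as well as HRV. The control-arm distress rule is the clearer source of unequal loss, because it applies to one arm only and operates expressly within the six weeks.

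What does not stand is the idea that existing text already closes the gap. No provision tells staff to offer the assessment to someone whom the study has removed, and analysis methods cannot recover values that were never collected.

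A reader might infer more: that outcome collection necessarily stops for everyone removed, that intent-to-treat is broken, or that the result is biased in a known direction. The documents support none of these. The Aim 2 dropout provision leaves room for a later biomarker assessment. Removed participants stay in their assigned arm with their baseline data. Nothing in the documents indicates the sign of any difference between removed and retained participants.

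**Conclusion.** The point stands as a cheap improvement and nothing heavier. As written, the rule would probably cost a participant removed between randomization and the post-treatment visit the primary outcome and the other week-7 measures. At the assumed rates the consequence is 0 to 6 people, a rise of about 0.02 SD in the detectable effect, and a bias of at most 0.05 SD in the HRV contrast (0.10 SD if the gaps run in opposite directions at the maximum rate in both arms). These bounds rest on two figures that are not in the documents: the 0% to 5% removal rate and the 1 SD ceiling on the unexplained gap. They do not include losses under the control-arm distress rule, for which the documents also give no rate.

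**What to change.** Keep the evaluation, referral and admission steps unchanged. Replace the removal clause with wording such as:

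*Withdrawn from study therapy or the waiting period; with consent and the treating clinician's agreement, randomized participants will be invited to complete the week-7 assessment (including Holter HRV if clinically able) and will be analyzed in the assigned arm.*

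Make the same separation in the WP-CON section: a control participant who takes immediate therapy leaves the waiting period, not the study, and is invited to the week-7 assessment.

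The cost is a sentence in each place with IRB approval, plus extra contacts with about 0 to 6 participants under the suicidality rule at the assumed rates and an unknown number under the distress rule. Courier collection of Holter monitors from participants' homes is already part of the protocol, which helps feasibility. The downside is that some people will decline or be too unwell, and some HRV values will reflect crisis care. Part of the data will still be missing, so the planned sensitivity analyses remain necessary.
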